### 11.2.3. Subgroup Analyses

Additional ancillary analyses on specific subgroup of subjects, may be presented.

These analyses will include but not limited to the following:

- Age (<60 versus  $\geq$  60 years);
- Gender (Male versus Female);
- Monitoring (Subjects with data from continuous ECG recording systems (eg. ILR, PM, ICD, CRT) versus those without).

### 11.2.4. Pooling Analysis

Center-to-center heterogeneity will be assessed for the primary endpoints by performing a random effects logistic regression analysis. Centers with less than five enrollments will be combined to form "supercenters". Small centers will be combined until the newly created supercenter has five enrollments, and then a new supercenter will be created. Centers will be deemed to be heterogeneous if the variance of the random center effect is found to significantly differ from zero. A significance level of 15% will be used for this test.

### 11.2.5. Multivariable Analyses

For each primary endpoint, univariate analyses of the following covariates will be performed, and any found to be significantly associated with the outcome at the .15 alpha

level will be included as covariates in a multivariate regression model. Backward selection with 0.15 alpha level stay criterion will be used to determine the final multivariate model. The list of baseline covariates includes, but is not necessarily limited to:

- Subject demographics (e.g. age, gender)
- Subject baseline characteristics (e.g. LVEF and LA diameter)
- Procedural techniques (e.g., esophageal temperature monitoring,)

An additional multivariable analysis will be performed to assess on the effect of cryo dosing parameters on acute (procedure duration, dwell time, acute success, acute adverse events) and chronic parameters (freedom from effectiveness failure). Cryo dosing parameters to be assessed for use in the model will be considered: number of cryo applications, time to isolation, ablation duration, sequence of veins approached and consecutive applications in the same vein. Additional subject variables such as PV anatomy and baseline characteristics will also be assessed for inclusion in the model.

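### The predictor models in section 11.2.5 (univariate screen at 0.15, then backward selection at 0.15) retain at least one covariate in about 42–56% of trials in which none matters, and their usual intervals would be invalid after selection

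*Combined protocol and SAP*

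**What the plan says.** Section 11.2.5 (Multivariable Analyses) gives one rule and applies it to both primary endpoints: "For each primary endpoint, univariate analyses of the following covariates will be performed". The entry condition is "any found to be significantly associated with the outcome at the .15 alpha" level. Elimination follows: "Backward selection with 0.15 alpha level stay criterion will be used to determine the final multivariate model".

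Five candidates are named as examples: age, gender, LVEF, LA diameter and esophageal temperature monitoring. The list is open: "The list of baseline covariates includes, but is not necessarily limited to".

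The section mentions no multiplicity adjustment, shrinkage, internal validation or limit on covariates per event. It does not say the model is exploratory, which regression form is used, or how estimates will be presented. Section 7.1, by contrast, calls the subgroup analyses non-powered, and section 11.2.3 calls its subgroup work ancillary.

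**The concern.** A threshold of 0.15 is liberal, and it is applied separately to every covariate on a list with no upper limit. Backward elimination at the same 0.15 looks like a second safeguard, but it barely raises the bar for covariates that have already passed it once. The survivors are then described as significantly associated and the result as the final model.

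At stake is how predictor findings will be read. Real-world usage is a stated objective (section 6.1), and procedural technique is among the candidates. A finding that temperature monitoring or LA diameter is associated with safety or effectiveness could be noise, and the usual error bars would not reveal it.

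**Working it through.** The plan states no error rate for this procedure, so there is no figure of its own to reproduce.

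**Inputs from the documents.** Entry level 0.15 and stay level 0.15 (11.2.5); five named covariates, list open (11.2.5); two primary endpoints; n = 199, the minimum for the primary tests (7.1, 7.2).

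**Assumptions.** Two-sided tests; logistic regression (11.2.5 says only a multivariate regression model); failure rate 35% for effectiveness; event rates of 3–9.5% for safety; about one third of subjects in one gender category; temperature monitoring used in 70–80%. The documents' own expected rates are blacked out.

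**1. Chance that some null covariate passes the screen.** For k independent covariates this is 1 − 0.85^k.
- k = 5: 1 − 0.444 = 55.6%
- k = 8: 72.8%
- k = 10: 1 − 0.197 = 80.3%

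**2. Effect of the backward step.** If elimination gets down to one covariate, the model is that covariate's univariate model, which has already passed at 0.15. So the step cannot empty a model that the screen filled. In every simulated setting, the share of trials with a non-empty final model equalled the share with any covariate passing the screen.

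**3. Full rule simulated under the null** (n = 199, five covariates, Wald tests, 3,000 trials per cell). Share of trials with a non-empty final model:

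| Event rate | Correlation 0 | 0.3 | 0.5 |
|---|---|---|---|
| 35% | 54.2% | 51.5% | 47.2% |
| 7% | 51.5% | 49.1% | 45.2% |
| 4% | 47.7% | 46.0% | 41.8% |

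At a 3% event rate with independent covariates it was 44.6%. With likelihood-ratio tests and independent covariates it was 55.0% (35% rate) and 52.8% (5% rate). A separate run with independent covariates gave 56%, 48% and 54% at event rates of 35%, 5% and 9.5%. Ten covariates gave 72–76% at correlation 0.3 and 77–80% when independent.

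**4. Intervals for retained noise covariates.** For one null covariate, P(p < 0.05 given p < 0.15) = 0.05/0.15 = 33%, so a conventional 95% interval covers the true value in 1 − 0.333 = 66.7% of retained cases. In the runs of step 3, coverage with five covariates was 59–72%, so 28–41% of intervals excluded no effect. A further null simulation gave 29–34%, against 4–5% in one full model fitted without selection.

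**5. What selection does and does not cause.** At least one retained noise covariate had p < 0.05 in about 14–22% of trials with five covariates. Testing five independent null covariates at 0.05 with no selection and no adjustment gives 1 − 0.95^5 = 22.6%. So dropping selection does not by itself lower this rate. With Holm adjustment in one full model it was 2–5%.

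**6. Events available for safety.** Section 11.1.1.3 requires the one-sided 95% log-log lower limit to exceed 86%. Without censoring, d events in 199 give S = 1 − d/199 and lower limit S^exp(1.645·se), where se² = [d/(199(199 − d))]/(ln S)².
- d = 19: S = 0.9045, se = 0.2295, limit 0.864, pass
- d = 20: S = 0.8995, se = 0.2237, limit 0.858, fail

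A passing study therefore has at most 19 safety events, or 19/5 = 3.8 per named covariate.

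**The case against.** The best defence is that this is a supplementary model on which no planned decision depends. The hypotheses in 11.1 are tested by Kaplan-Meier limits against 86% and 50%, and the objectives table in section 6.2 lists no predictor objective. A 0.15 level is a familiar screen for generating hypotheses. That limits the weight of the point, but 11.2.5 does not present the model in that way.

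Several stronger readings are tempting and are not supported:
- **That the plan commits to reporting faulty confidence intervals.** Section 11.2.5 does not mention intervals. The point applies to conventional model output if it is presented, and the fault lies in selection (estimates pushed away from zero, search ignored), not simply in interval width.
- **That safety is the worse case.** On the quantities measured, safety is slightly better: 47.7% at a 4% event rate against 54.2% at 35%. Instability from sparse events is a reasonable worry but was not quantified, and 19 is a ceiling for passing, not an expected count.
- **That false predictors will be announced in half of null trials.** Retention in a model is not a published claim.
- **That removing selection alone cures false positives.** Step 5 shows that the reduction comes from Holm.

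It is also fair to say that the rate falls below half when covariates are correlated or events very few, and that the five covariates are only examples.

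**Conclusion.** The point holds as an inexpensive improvement. Under the stated rule, with the five named covariates and no true effects, a final model with at least one predictor arises in about 42–56% of trials, rising to about 80% with ten candidates. About one third of retained noise covariates would have a conventional 95% interval excluding no effect, where 5% is intended. These figures rest on the assumed logistic form, event rates, covariate prevalences and correlations. The one-third figure also follows directly from 0.05/0.15, so it depends little on them.

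A reader might infer that the study's primary conclusions are compromised. They are not: the performance-goal tests do not use these models. The consequence is confined to what may be said about predictors of the two primary endpoints.

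**What to change.** Amend 11.2.5 before analysis, by the route that 11.2.7 already provides.

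- **Primary effectiveness:** replace screening and elimination with one prespecified model containing age, gender, LVEF, LA diameter and esophageal temperature monitoring. Report every estimate with its 95% confidence interval. Without selection the intervals return to roughly nominal coverage.
- **Primary safety:** do no stepwise selection. Report Firth-penalised estimates with 95% intervals as descriptive. If they are given one covariate at a time, state that they are unadjusted. This matters for temperature monitoring, which section 10.5.1.1 recommends but does not assign, so its association with outcome may be confounded.
- **Wording:** label both models, and any covariate added later, as exploratory. Do not call a covariate significantly associated at 0.15. If a significance statement is wanted, base it on a multiplicity-adjusted p-value such as Holm, and say that the accompanying intervals are unadjusted.

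The cost is SAP wording and a few lines of code, with no new data. The drawbacks are less sensitivity to weak predictors and no search beyond the five named covariates in the main model. This change does not cover the separate cryo-dosing analysis in the same section, which states no selection rule.

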#### **10.5.1.2. *Phrenic Nerve Activity Monitoring***

During ablation, phrenic nerve activity monitoring will be performed according to the standard of care at the site. It is highly recommended to use the Diaphragm Movement Sensor. If the Diaphragm Movement Sensor (DMS) is used, data will be collected in the eCRF. If a reduction in phrenic response is detected, the operating physician will continue to closely monitor phrenic nerve activity and pacing capture, and will consider immediately interrupting cryoablation. In case of phrenic nerve injury at the procedure the subject status and potential resolution of the adverse event will be monitored during the course of the study.

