#### 11.2.6. Additional Analyses

Additional analyses include, but are not limited to:

- Procedure times: LA dwell time\*, total ablation time, number of cryo applications per vein, time to thaw, total fluoroscopy time and total procedure time;
- Time-To-Isolation per ablation application, if available;
- Freedom from recurrence of individual types of atrial arrhythmias (AF, AFL, AT) between days 91 and days 365 post-index procedure;
- Analysis of ablation techniques (i.e. segmental approach to left common trunk, additional linear ablations, etc.);
- Analysis of different anaesthesia techniques (General anaesthesia with or without intubation versus sedation)
- Freedom from recurrence in subjects with non-common anatomical configurations of PV (e.g. left common trunk);
- Freedom from primary effectiveness failure evaluated in subgroups of subjects (termination of AAD versus continuation of AAD after blanking period);
- For the subgroup of subjects undergoing 3D mapping with the Boston Scientific mapping Rhythmia system and performing a post-procedural map, map information will be collected to determine lesion locations;
- For subjects that will undergo repeat ablation during the course of the clinical follow-up, anatomical location of ablations gaps will be assessed.

\* LA dwell time is defined as time from the Cryoablation Catheter introduced in the left atrium (LA) to the last time of Cryoablation Catheter exiting the LA.

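### The technique and anaesthesia analyses in 11.2.5 and 11.2.6 name no centre term, so where a technique follows site practice, site differences can be mistaken for technique effects

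*Combined protocol and SAP*

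**What the plan says.** **Multivariable models (11.2.5).** For each primary endpoint, candidate covariates are tested one at a time at 0.15, and then "Backward selection with 0.15 alpha level stay criterion will be used to determine the final multivariate model". The candidates are demographics, baseline characteristics and "Procedural techniques (e.g., esophageal temperature monitoring". The list is open: "The list of baseline covariates includes, but is not necessarily limited to". A second model relates cryo dosing parameters to acute and chronic outcomes; for further adjustment it says only that "Additional subject variables such as PV anatomy and baseline characteristics will also be assessed for inclusion in the model". Centre and operator are not named in either model.

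**Technique comparisons (11.2.6).** Two items are listed as topics, with no model, test or adjustment: "Analysis of ablation techniques (i.e. segmental approach to left common trunk, additional linear ablations, etc" and "Analysis of different anaesthesia techniques (General anaesthesia with or without intubation versus sedation".

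**Centre (11.2.4).** "Center-to-center heterogeneity will be assessed for the primary endpoints by performing a random effects logistic regression analysis". Centres with fewer than five enrolments are merged into supercenters, and the test level is 15%. No consequence of a positive result is stated, and nothing links this analysis to 11.2.5 or 11.2.6.

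**What decides the technique.** Section 10.5.1.2 says that "phrenic nerve activity monitoring will be performed according to the standard of care at the site". Section 7.3 ties adjunctive ablation to site standard of care. Oesophageal temperature monitoring is strongly recommended but not required (10.5.1.1). The anaesthesia method is only recorded (10.5.5).

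**The concern.** If a site does most of its cases one way, comparing techniques largely means comparing one group of sites with another. Two things then go wrong. First, operator experience, case mix and detection habits differ between sites and become mixed with the technique contrast. The protocol makes this link itself: section 5.1.5 relates the incidence of phrenic nerve injury to experience with the procedure, and persistent phrenic nerve injury is a component of the primary safety endpoint. Second, outcomes within a site are correlated, so a standard error that treats subjects as independent is too small.

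Real-world usage is the study's stated secondary objective, and the technique and anaesthesia analyses appear among the additional endpoints in the synopsis. A reader will take an association from these models as information about the technique.

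**Working it through.** The plan states no figure on this point, and its sample-size sections are blank or redacted, so there is nothing of the plan's to reproduce beyond the centre cap in 11.3.3 (10% of 199 = 19.9, i.e. 20).

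**Inputs from the documents.** 199 analysed subjects; about 25 centres; initial cap of 20 per centre; selection level 0.15.

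**Assumptions.** The documents do not give the between-centre variation or how closely technique follows site, so both are varied. The event-free rate is taken as about 65–70%, in line with the efficacy that section 4.1 cites for the existing cryoballoon.

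**Step 1: design effect, technique fixed by site.** Mean centre size m = 199/25 = 7.96. DE = 1 + (m − 1) × ICC. The true standard error is √DE times the reported one, and the false-selection rate at a nominal 0.15 is 2 × [1 − Φ(1.440/√DE)].

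| ICC | DE | √DE | False-selection rate |
|---|---|---|---|
| 0 | 1.00 | 1.00 | 0.150 |
| 0.02 | 1.14 | 1.07 | 0.177 |
| 0.05 | 1.35 | 1.16 | 0.215 |
| 0.10 | 1.70 | 1.30 | 0.269 |

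If enrolment expands to 400, m = 400/25 = 16 and the design effect at ICC 0.05 becomes 1 + 15 × 0.05 = 1.75.

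**Step 2: simulation by centre SD.** 199 subjects, 25 unequal centres of at most 20, no true technique effect, two-sample z test. Centre SD σ is on the log-odds scale; ICC = σ²/(σ² + π²/3), so SDs of 0.3, 0.5 and 0.7 correspond to ICCs of 0.03, 0.07 and 0.13.

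| Subjects on their site's usual technique | No centre effect | SD 0.3 to 0.7 |
|---|---|---|
| 100%, passes 0.15 | 15.0% | 19%, 25%, 31% (SD 0.3, 0.5, 0.7) |
| 100%, significant at 0.05 | 4.8% | 7.7%, 11.3%, 16.7% (same SDs) |
| 90%, passes 0.15 | about 15% | about 18–25% |
| 70%, passes 0.15 | about 15% | about 15–17% |

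**Step 3: separate simulation, with and without centre.** Event-free rate 0.70, 1,500 runs per setting (Monte Carlo error √(0.15 × 0.85/1500) ≈ 0.009), nominal 0.15.

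| ICC | Fixed by site, no centre term | 90%, no centre term | 90%, stratified by centre | 70%, no centre term |
|---|---|---|---|---|
| 0.02 | 0.168 | 0.170 | 0.160 | 0.151 |
| 0.05 | 0.231 | 0.199 | 0.157 | 0.174 |
| 0.10 | 0.276 | 0.212 | 0.141 | 0.183 |

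Stratifying by centre brings the rate close to nominal. When technique is wholly fixed by site, the stratified test has no information, because centre and technique are aliased.

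**Step 4: can the safety models carry a centre term?** At the 86% goal, 199 × 0.14 ≈ 28 subjects would have an event, about 28/25 ≈ 1.1 per centre, and fewer if the device performs better than the goal. A random intercept may not be estimable there.

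**The case against.** **Technique is not shown to be set by site for everything analysed.** This stands. A reader might infer that site standard of care fixes all these choices. The documents say so only for adjunctive ablation and phrenic nerve monitoring, and the latter is not named in 11.2.5 or 11.2.6. Anaesthesia is only recorded, and oesophageal temperature monitoring is a study-wide recommendation. The segmental approach depends on the subject's anatomy (10.5.2.1), and even adjunctive ablation is partly attributed to what is found in the individual subject (7.3; Table 6.2-1). All of these can vary within a site.

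**The plan does not exclude centre.** True: the 11.2.5 list is open, and 11.2.7 allows the SAP to be amended before analysis. But an open list leaves the decision until results may be known.

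**No p-value in 11.2.6 can be called too small.** Correct: that section specifies no model or test. The point there is that the comparison should be specified with centre in it.

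**The analyses are exploratory and the screen is lenient.** Also correct. The subgroup analyses are declared non-powered, and at 70% site adherence the inflation is barely visible. This limits the weight of the point but does not remove it.

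**A random intercept does not cure confounding.** This stands, and it shapes the fix. A random intercept assumes that the centre effect is independent of technique. It corrects the standard error but does not by itself remove between-site confounding.

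**Conclusion.** The point holds as a cheap improvement to exploratory analyses. The plan names centre only in a heterogeneity test that feeds nothing else, and 11.2.5 followed as written screens techniques as if subjects were independent.

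The size depends on two quantities that the documents do not give: between-centre variation and how closely technique follows site. The steps above span a range from no inflation (no centre effect) to roughly twice the nominal 0.15 (SD 0.7, technique wholly fixed by site). The simulations test a single unadjusted comparison, not the whole backward-selection procedure.

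Two stronger readings are not supported. One is that site differences will be reported as technique effects: they can be, but nothing in the documents shows that they will. The other is that the study's main conclusions are at risk: both primary tests compare a Kaplan-Meier lower confidence limit with a fixed goal and contain no technique term.

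**What to change.** Amend the SAP under 11.2.7 before analysis:

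1. In 11.2.5, including the cryo dosing model, and in any technique or anaesthesia comparison under 11.2.6, include a random intercept for centre (a shared frailty if the model is for time to event).
2. Use actual centres, not the merged supercenters of 11.2.4, which can combine sites with different practice.
3. Where events are too few for a random intercept, as may happen for safety, use centre-clustered standard errors, and state this fallback in advance.
4. Tabulate each technique by centre.
5. Where a technique varies within centres, report the within-centre contrast, for example stratified by centre.
6. Label every other technique result as a descriptive between-site comparison.

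**Cost.** SAP wording and some programming; no new data or subjects. Intervals for technique effects will be wider, the sparse safety models may fail to converge, and techniques fixed by site will yield only a descriptive statement.

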#### 11.2.6. Additional Analyses

Additional analyses include, but are not limited to:

- Procedure times: LA dwell time\*, total ablation time, number of cryo applications per vein, time to thaw, total fluoroscopy time and total procedure time;
- Time-To-Isolation per ablation application, if available;
- Freedom from recurrence of individual types of atrial arrhythmias (AF, AFL, AT) between days 91 and days 365 post-index procedure;
- Analysis of ablation techniques (i.e. segmental approach to left common trunk, additional linear ablations, etc.);
- Analysis of different anaesthesia techniques (General anaesthesia with or without intubation versus sedation)
- Freedom from recurrence in subjects with non-common anatomical configurations of PV (e.g. left common trunk);
- Freedom from primary effectiveness failure evaluated in subgroups of subjects (termination of AAD versus continuation of AAD after blanking period);
- For the subgroup of subjects undergoing 3D mapping with the Boston Scientific mapping Rhythmia system and performing a post-procedural map, map information will be collected to determine lesion locations;
- For subjects that will undergo repeat ablation during the course of the clinical follow-up, anatomical location of ablations gaps will be assessed.

\* LA dwell time is defined as time from the Cryoablation Catheter introduced in the left atrium (LA) to the last time of Cryoablation Catheter exiting the LA.

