#### 10.4.1. Medications

##### 10.4.1.1. Anti-Arrhythmic Drugs

Information on all Anti-arrhythmic drug (AAD) medications will be collected on the eCRF starting from baseline visit. During the entire course of the study, details on changes will be specified on the eCRF. Post-index procedure AADs are allowed per investigator's discretion during the blanking period (90 days post-index procedure). According to HRS consensus guidelines (11), it is recommended to stop the administration of AAD for any atrial tachyarrhythmia after blanking period. If the investigator determines that the subject must be prescribed an increased dosage of AAD or a new AAD for treatment of any atrial tachyarrhythmia after the blanking period, the subject will be considered a Primary Effectiveness Failure.

*AADs for endpoint will consist of all Class I/III and any Class II/IV medications taken for control of AF/AFL/AT recurrence.*

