### 11.1.2. Primary Effectiveness Endpoint

The primary effectiveness endpoint will be evaluated by the failure-free rate at 12 months post-index procedure in each cohort.

*Failure defined as:*

- Failure to achieve acute procedural success\* in the index procedure;
- More than one repeat procedure during the blanking period (within 90 days post-index procedure);
- Documented atrial fibrillation, or new onset of atrial flutter or atrial tachycardia event ( $\geq 30$  seconds in duration or from a 10 second 12-lead ECG) between days 91 and days 365 post-index procedure\*\*.
- Any of the following interventions for atrial fibrillation, or new onset of atrial flutter or atrial tachycardia between days 91 and days 365 post-index procedure:
  - Repeat procedure
  - Electrical and/or pharmacological cardioversion for AF/AFL/AT
  - Prescribed a higher dose of any AAD\*\*\* documented at baseline or a new AAD\*\*\* not documented at baseline

\* Acute procedural success is defined as isolation of the all pulmonary veins or anatomical equivalents achieved with the POLARx Cryoablation balloon at the end of the index procedure and as demonstrated at minimum by entrance block using the Cryo Mapping Catheter (Other techniques of assessment are per investigator's discretion)

\*\* Subjects will be monitored for recurrences of the arrhythmias by means of clinical visits, ECG and 24-hour Holter monitoring. Recurrences documented with other devices only (eg. ILR, PM, ICD, CRT) will not be counted as primary effectiveness endpoint events

\*\*\* AADs for endpoint will consist of all Class I/III and any Class II/IV medications taken for control of AF/AT/AFL recurrence

[figure not shown]

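### The comparison of AAD termination versus continuation sets no classification date and does not require subjects to be failure-free; grouping on behaviour after blanking would add immortal-time bias

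*Combined protocol and SAP*

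**What the plan says.** The synopsis and Sections 6.2.4 and 11.2.6 list the same analysis: "Freedom from primary effectiveness failure evaluated in subgroups of subjects (termination of AAD versus continuation of AAD after blanking period". The groups are described only by those closing words.

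- **Outcome.** Under Section 11.1.2, the recurrence and intervention components are counted "between days 91 and days 365 post-index procedure". The composite also includes "Failure to achieve acute procedural success" at the index procedure and more than one repeat procedure during blanking.
- **How AAD use is decided.** Section 10.4.1.1 states that "Post-index procedure AADs are allowed per investigator's discretion during the blanking period", and that afterwards "it is recommended to stop the administration of AAD for any atrial tachyarrhythmia after blanking period". This is a recommendation, so who stops, and when, is left to the investigator. After blanking, a subject who "must be prescribed an increased dosage of AAD or a new AAD" is a failure.
- **Month 3 rule.** Section 10.8 treats AAD changes made at the Month 3 visit (day 77 to day 105) as falling within blanking. It gives the endpoint's medication requirement as a reason and does not mention these subgroups.
- **Method.** The only method stated for this endpoint is the 365-day Kaplan-Meier rate in Section 11.1.2.3. No landmark, time-dependent or adjusted analysis is given for this comparison.

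**The concern.** The groups are named by what happens to the drug after blanking, which is also the period in which most failure components are counted. If any stop after blanking puts a subject in the termination group, a subject who stops at Month 6 while failure-free is credited with failure-free time from day 91 to day 180. A subject who fails on day 120 while on drug and is not later recorded as stopping is counted as a continuer. Acute failures and multiple blanking-period repeat procedures come before either label, yet they enter the comparison too.

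The consequence is a possible difference between the groups that has nothing to do with AADs and that more data would not remove. Section 21 commits the sponsor to submit results for publication. Leaving the classification date open also allows it to be chosen after the data have been seen.

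**Working it through.** The plan gives no figure for this comparison, so there is nothing to reproduce. The check asks what gap appears when AADs have no effect.

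**Inputs from the documents.** The outcome window is days 91 to 365 (274 days), with visits at nominal days 91 and 180. Section 4.1 gives about 70% and 65% efficacy in earlier cryoballoon studies; 65% is used here.

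**Assumptions (not in the documents).** All subjects compared are on an AAD at day 91. The failure hazard is constant from day 91. Stopping is unrelated to prognosis. A fraction a stops at Month 3. A fraction b of those still on drug and failure-free stops at Month 6.

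**1. Grouping by any stop after blanking**

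- Failure-free at day 180: 0.65^(89/274) = 0.869
- Share terminated: A = a + (1 − a) × 0.869 × b
- Failure-free, terminated: 0.65 × [a + (1 − a)b] / A
- Failure-free, continued: 0.65 × (1 − a)(1 − b) / (1 − A)

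Example, a = b = 0.5: A = 0.5 + 0.5 × 0.869 × 0.5 = 0.717. Terminated: 0.65 × 0.75 / 0.717 = 68.0%. Continued: 0.65 × 0.25 / 0.283 = 57.5%.

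| a (Month 3) | b (Month 6) | Terminated | Continued | False gap (points) | Reversal share q |
|---|---|---|---|---|---|
| 0.7 | 0.1 | 65.4% | 64.1% | 1.3 | 4% |
| 0.5 | 0.2 | 66.4% | 62.9% | 3.5 | 9% |
| 0.3 | 0.3 | 68.7% | 61.6% | 7.1 | 14% |
| 0.5 | 0.5 | 68.0% | 57.5% | 10.5 | 27% |
| 0.7 | 0.7 | 67.0% | 49.8% | 17.2 | 47% |
| 0 | 0.5 | 74.8% | 57.5% | 17.3 | 27% |

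The last row applies if only stops later than Month 3 count as being after blanking. With 0.70 in place of 0.65 (and 0.891 for 0.869), the range is about 1 to 16 points.

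**2. When the sign reverses.** Suppose a share q of the failures in the continued group is later recorded as terminated. Let F_T and F_C be the failures in the two groups as fractions of all subjects. The gap is zero when q = (0.35A − F_T) / (0.65 × F_C). For a = b = 0.5, F_T = 0.7174 − 0.4875 = 0.2299 and F_C = 0.2826 − 0.1625 = 0.1201. So q = (0.2511 − 0.2299) / 0.0781 = 27%. The last column of the table gives q for each row.

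**3. Grouping by Month 3 status instead.** With stopping unrelated to prognosis and no earlier failures, both groups are at 65% and the gap is zero. Two problems remain.

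- *Failures before the grouping.* Assume a fraction x fails acutely and stops with probability 0.3, against 0.6 in the others, with the overall failure-free rate held at 65%. Share terminated: n = 0.3x + 0.6(1 − x). Rates: 0.6 × 0.65 / n and 0.4 × 0.65 / (1 − n). For x = 2%, n = 0.594: 65.7% vs 64.0%, a gap of 1.6 points. For x = 10%, n = 0.570: 68.4% vs 60.5%, a gap of 8.0 points.
- *Confounding by indication.* Assume 30% recur during blanking and stop half as often, with half of all subjects stopping. The stopping probabilities are then 0.5 / 0.85 = 0.588 and 0.294. With a doubled hazard after recurrence, 0.7y + 0.3y² = 0.65 gives y = 0.712 and y² = 0.506. Terminated: (0.7 × 0.588 × 0.712 + 0.3 × 0.294 × 0.506) / 0.5 = 67.5%. Continued: 62.5%. The gap is 5.1 points. With a tripled hazard (y = 0.749, y³ = 0.420) the rates are 69.1% and 60.9%, a gap of 8.1 points.

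**The case against.** The strongest reply is that the wording can naturally mean AAD status as blanking ends. Section 10.4.1.1 recommends stopping then, and Section 10.8 places Month 3 changes inside blanking. Under that reading there is no immortal time. This stands as a possible reading, but the plan does not adopt it: the Month 3 rule does not define these groups. Applied literally, that rule would make termination after blanking mean later stops only, as in the last row of the table.

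A reader might infer that the planned comparison is biased in a known direction and will make stopping look beneficial. The documents do not support that. Nothing in them says that only failure-free subjects stop. A subject may recur, have a repeat ablation and then stop, and enough such cases reverse the sign. At the low stopping rates, 4% to 9% of on-drug failures would be enough.

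The size is also assumption-dependent. If most stopping happens at Month 3, the gap is 1 to 4 points. With 120 subjects (also an assumed number), the standard error of the difference in those scenarios is about 9 to 10 points.

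Overlap between the grouping and the outcome is limited too. Only a higher dose or a new AAD is a failure; termination and unchanged continuation are not.

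Finally, this is one additional analysis with no hypothesis attached, and Section 7.1 calls the subgroup analyses non-powered. That lowers the priority, but lack of power does not make a biased comparison interpretable.

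**Conclusion.** The point holds as a defect of definition with a conditional bias. The plan fixes neither the classification date nor a failure-free requirement. If subjects are grouped by AAD behaviour at any time after blanking, immortal time would usually favour termination, by about 1 to 17 points with no AAD effect. That range assumes a 65% failure-free rate, a constant hazard, stopping only at the Month 3 and Month 6 visits while failure-free, and the stopping rates in the table; the documents give no stopping rates. Reversal is possible.

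A reader might also infer that Month 3 grouping cures the problem. It removes the immortal time. It still keeps failures that precede the grouping unless they are excluded, and it leaves confounding by indication (5 to 8 points in the example). Neither primary hypothesis test is affected. The change is worth making before the analysis but does not bear on the trial's main conclusions.

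**What to change.** Specify in the SAP:

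1. Restrict the comparison to subjects who took an AAD during blanking. Month 3 status alone would mix those who never took one with those who terminated.
2. Classify each as terminated or continued by AAD status recorded at the Month 3 visit, including changes made at that visit.
3. Include only subjects failure-free at the landmark, defined as the later of day 91 and that visit. This removes acute failures, multiple blanking-period repeat procedures and failures up to day 105 where the visit is late.
4. Start the Kaplan-Meier clock at the landmark and do not reclassify for later changes. Later changes enter only as a time-dependent covariate in a supporting model.
5. Adjust for, or stratify by, arrhythmia recurrence during blanking.
6. Report the result as descriptive and state that confounding by indication remains.

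The cost is SAP wording, which Section 11.2.7 allows before the analysis. AAD changes are already collected at Month 3. A few early failures drop out of this exploratory comparison. The change concerns analysis only and says nothing about how AADs should be managed.
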